Subjects will be assessed at every visit for adverse events (AEs) and concomitant medications, starting from the first dose of study treatment. Toxicity severity will be graded according to the National Cancer Institute Common Terminology Criteria for Adverse Events (NCI CTCAE) v 5.0. Additional safety assessments conducted periodically throughout the study will include vital signs, physical examinations, ECOG PS, ECHO (or other methods according to institutional practice) for determination of LVEF (only if clinically indicated), ECGs, and clinical laboratory assessments (hematology, serum chemistry, and urine pregnancy test).

Blood samples for PK/PD assessments will be drawn over a 6-hour period on C1D1 and C2D1.

Additional blood samples for PK/PD assessments will be drawn at 2 hours (± 10 minutes) post-dose on C1D15, pre-dose (within 30 minutes) on C3D1 and Day 1 of every cycle thereafter, and at any time during the EOT Visit.

Subjects may continue with their study treatment until disease progression, development of other unacceptable toxicity, confirmed pregnancy, death, withdrawal of consent, until the subject is lost to follow-up, or the Sponsor ends the study, whichever occurs first.

Upon radiographic disease progression, PIs, with consult from the Sponsor, may keep the subjects on ivosidenib after the disease progression provided the subject is clinically benefitting and there is no contraindication to continuing treatment beyond progression.

Post-Treatment Follow-up Visit: A Post-Treatment Follow-Up Visit for safety will occur 28 days (no more than 33 days) after the last dose of study drug. Every effort must be made to perform protocol-specified evaluations unless consent to participate in the study is withdrawn. If a subject's dose is interrupted for 28 days and then the subject discontinues study participation, the EOT Visit will serve as the Post-Treatment Follow-up Visit.

PFS and Survival Follow-up: Subjects who discontinue study treatment for reasons other than disease progression or withdrawal of consent will be followed in PFS follow-up with the same schedule of assessments as before study treatment discontinuation, until documented disease progression the initiation of new anti-cancer therapy, death, withdrawal of consent, or the end of study/study termination, whichever occurs first. If a subject begins a new anticancer therapy during PFS follow-up, information on the new anticancer therapy will be collected.

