5.5. Participant withdrawal

5.5.1. Withdrawal criteria

Subjects have the right to withdraw from the study at any time for any reason. A subject's discontinuation of study treatment or withdrawal from the study will not jeopardize the relationship with their healthcare providers or affect their future care. This decision must be recorded in writing by the study site.

Premature discontinuation of IMP does not mean that the subject prematurely stops the participation in the study.

Subjects discontinuing study treatment for reasons other than withdrawal of consent from overall study participation will be expected to continue in the study including safety follow-up visits and be contacted for survival follow-up.

Should a subject decide to withdraw, all efforts will be made to complete and report the protocol defined study observations as completely as possible and to determine the reason for withdrawal.

In the event a subject discontinues study treatment or withdraws from the study, the Sponsor must be informed. If there is a medical reason for withdrawal, the subject will remain under the supervision of the Investigator until satisfactory health has returned.

When a subject discontinues study treatment or withdraws from the study, the primary reason for discontinuation or withdrawal must be recorded in the appropriate section of the electronic case report form (eCRF) and all efforts will be made to complete and report final study observations as thoroughly as possible.

Criteria for premature discontinuation of IMP are:

Subjects may discontinue or be discontinued from study treatment at any time. In this situation, a subject without documented progressive disease by the Investigator should be followed for tumor assessments until the development of progressive disease and/or survival.

The reasons for premature study treatment discontinuation are:

- Adverse events, according to the judgment of the Investigator, including no recovery in safety parameters
- Certain adverse events (as described in [Section 8.11.1](#) including instances of Grade 4 QTcF prolongation.
- Disease progression (subjects who are, in the opinion of the Investigator, benefitting from treatment [e.g., slow progression] may be allowed to continue study treatment with approval of the Sponsor)
- Physician decision (for reasons that cannot be included in any of the criteria listed above)
- Pregnancy (for reporting see [Section 8.8](#)),

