OS follow-up assessments will occur approximately every 12 weeks after EOT unless the subject is in PFS follow-up at that time. If a subject progresses or does not come back for scans while in PFS follow-up, then the OS follow-up assessments will begin at the next planned OS follow-up time point, following the schedule of every 12 weeks. OS follow-up will assess survival status and documentation of receipt and type of subsequent anticancer therapy unless consent to participate is withdrawn. If a subject begins a new anticancer therapy during PFS follow-up, information on the new therapy will need to be entered. OS follow-up will continue until all subjects have died, withdrawn consent, or are lost to follow-up, up to 24 months after the last subject enrolled, whichever occurs first. HRQOL (until the start of new anticancer therapy) assessments will be collected every 12 weeks after EOT.

All scans should be sent to the IRC, as detailed in the site-specific Imaging Core Manual. A central review of collected images may be conducted by an independent review committee. This independent review will not be used for treatment decisions.

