10.2. Determination of sample size

Approximately 10 Japanese subjects will be enrolled in the study.

The primary endpoint is PFS status (as assessed by IRC per RECIST v1.1) at 6 months after Day 1 (C1D1). Assuming a target 6-month PFS rate of 32% and a dropout rate of 10%, the study needs to enroll 10 subjects to provide approximately 84% power to reject the null hypothesis of PFS rate \leq 2.6% using exact binomial test at 1-sided significance level of 0.05.

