#### 5.3.1. Primary efficacy endpoint

The primary analysis will be performed on the ITT set.

The progression-free survival (PFS) by IRC is defined as the time in months from Day 1 (C1D1) to the date of the first documentation of disease progression as determined by the IRC per RECIST v1.1 or death due to any cause, whichever occurs first.

PFS = (Earliest Date of Disease Progression or Death – Day 1 Date + 1) / 30.4375.

The primary endpoint is PFS status at 6 months after Day 1 (C1D1). The 6-month PFS rate defined as the probability of subjects who are alive and progression-free at 6 months after Day 1 (C1D1) will be used to assess the primary endpoint. Kaplan-Meier method will be used to estimate the 6-month PFS rate. Exact binomial test with 1-sided significance level of 0.05 will be used to compare the 6-month PFS rate against 2.6%.

Subjects without documentation of disease progression or death at the time of the analysis of PFS will be censored at the date of the last response assessment prior to the start of alternate therapy. See [Table \(5.3.1\) 1](#) for the details on handling of missing response assessments and censoring.

Number of subjects with events, types of events (progression or death), and number of subjects censored, number of subjects for each reason of censoring, Kaplan-Meier estimates, and 95% CIs according to Brookmeyer and Crowley method for the median, Q1 and Q3 for PFS will be presented. Probabilities of event free at selected time points, such as 3-month, 6-month, 9-month, and 12-month, will be presented. Kaplan-Meier curves of PFS will be provided with the number of subjects at risk over time included.

In addition, the concordance of PFS between investigator and IRC assessment will also be summarized.

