**Table (5.3.1) 1 Handling of Missing Response Assessment and Censoring for the Primary Analysis of PFS**

Situation	Date of Censoring
No baseline assessment and no death.	Date of the Cycle 1 Day 1
Alternate anticancer systemic treatment started before documented progression (PD) per RECIST 1.1 or death.	Date of last adequate assessment prior to the start of alternate anticancer treatment 
No adequate post-baseline assessment and no death.	Date of the Cycle 1 Day 1
No documented PD per RECIST 1.1 or death before data cut-off date or before permanently discontinued from the study.	Date of last adequate assessment 

Situation	Date of Censoring
Documented PD per RECIST 1.1 or death following a long gap from the previous adequate assessment (e.g., 2 or more consecutive missed scheduled disease status assessments). The long gap is defined as $\geq 95$ days (ie, 12 weeks + 10 days per the protocol defined visit window). If no adequate assessment prior to minimum of (PD, death), the long gap is calculated from the Cycle 1 Day 1.	Date of last adequate assessment prior to the first occurrence of 2 or more consecutive missing scheduled assessments

 Adequate disease assessment is defined as a response assessment other than “not evaluable.” If there is no adequate response assessment prior to the start of anticancer treatment, it will be censored at the date of Cycle 1 Day 1.

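### Subjects taken off drug for Investigator progression that the IRC has not called are censored in the primary Kaplan-Meier analysis, which can bias the 6-month PFS rate upward

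*Protocol*

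**What the plan says.** **Event.** SAP 5.3.1 dates primary PFS to "the first documentation of disease progression as determined by the IRC per RECIST v1.1 or death due to any cause, whichever occurs first". The 6-month rate is estimated by Kaplan-Meier, and the test is described as "Exact binomial test with 1-sided significance level of 0.05 will be used to compare the 6-month PFS rate against 2.6" per cent.

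**Who is scanned after stopping drug.** Protocol 4.1.1: "Subjects who discontinue study treatment for reasons other than disease progression or withdrawal of consent will be followed in PFS follow-up". Protocol 5.5.1 names the assessor: "a subject without documented progressive disease by the Investigator should be followed for tumor assessments". On the IRC, Protocol 7.2 adds: "This independent review will not be used for treatment decisions". Nothing requires the IRC to agree before imaging ends.

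**Exception.** Protocol 7.2 and 8.10.1.3 keep imaging on schedule for subjects who stay on ivosidenib beyond radiographic progression. Under 8.10.1.2 that ends with clinical deterioration or further radiographic progression, and the subject then moves to survival follow-up.

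**Censoring.** SAP Table (5.3.1) 1 has no row for Investigator progression without IRC progression. Such a subject falls under "No documented PD per RECIST 1.1 or death before data cut-off date or before permanently discontinued from the study", or under the row for alternate systemic treatment. Both censor at the last adequate assessment. The long-gap row censors a progression or death that follows that assessment by 95 days or more. The rows do not say whose progression call is meant.

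**Sensitivity.** SAP 5.3.1.1 offers only an optional per-protocol analysis by the same method. Investigator/IRC concordance (5.3.1) and PFS per Investigator (5.3.2.2) are also reported.

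**The concern.** One assessor ends the imaging and another defines the event. When the Investigator calls progression and the IRC does not, the subject leaves the IRC risk set because progression is suspected. Kaplan-Meier then treats that subject's remaining risk as equal to that of subjects still being scanned. If the Investigator's call tends to precede the IRC's, imminent events are removed and the estimated 6-month rate rises.

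The long-gap row adds to this. Suppose the last adequate scan is at week 6 (day 42) or week 12 (day 84). A death from day 42 + 95 = 137, or from day 84 + 95 = 179, is then censored although it falls before 6 months (6 × 30.4375 = 182.6 days). A subject known to be dead at 6 months would not count as an event.

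At stake is the headline estimate of an open-label, single-arm trial of about 10 subjects. It will be read against a fixed 2.6%, and one or two subjects move it visibly.

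**Working it through.** **1. The plan's own figure.** Protocol 10.2: "Assuming a target 6-month PFS rate of 32% and a dropout rate of 10%, the study needs to enroll 10 subjects" for "approximately 84% power to reject the null hypothesis of PFS rate" at or below 2.6%, one-sided 0.05. With 10 × 0.9 = 9 evaluable and success at 2 or more:
- alpha = 1 − 0.974^9 − 9(0.026)(0.974^8) = 0.0216
- power = 1 − 0.68^9 − 9(0.32)(0.68^8) = 0.837, which matches 84%

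With all 10 the values are 0.0265 and 0.879. The stated power therefore takes dropouts out of the denominator.

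**2. Worked Kaplan-Meier example.** This is an illustration with n = 10 and IRC progression at weeks 6, 6, 6, 12, 12, 18, 24, 36, 42, 48. Three subjects are progression-free at 6 months.
- No discordance: 7/10 × 5/7 × 4/5 × 3/4 = 30%.
- One week-12 progressor censored at week 6: 7/10 × 5/6 × 4/5 × 3/4 = 35%.
- Also the week-18 progressor censored at week 12: 7/10 × 5/6 × 3/4 = 44%.
- Also the week-24 progressor censored at week 18: 7/10 × 5/6 = 58%.

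**3. Expected size.** Inputs from the documents: 6-weekly scans, so four scans (weeks 6 to 24, day 168) precede 6 months and the next is at day 210; n = 10; rates 32% and 2.6%. Assumptions: constant hazard; a share q of subjects is called by the Investigator one scan before IRC progression and censored there; none of them is scanned again or dies inside the 95-day window.

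With true rate p, the per-scan IRC hazard is h = 1 − p^(1/4). From scan 2 on, the hazard Kaplan-Meier sees is h(1 − q)/(1 − hq), so in large samples it estimates p/(1 − hq)^3. For p = 0.32, h = 0.248:
- q = 0.10: 0.32/0.9752^3 = 34.5%
- q = 0.20: 0.32/0.9504^3 = 37.3%
- q = 0.30: 0.32/0.9256^3 = 40.4%

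Simulation at n = 10 gives 34.5%, 37.4% and 40.1%. At p = 0.026 (h = 0.598) the formula gives 3.1%, 3.8% and 4.7%. Simulation at n = 10 gives 3.5%, 4.7% and 6.0%, higher because a small risk set can empty on a censored subject.

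**4. Softer assumptions, true 32%, q = 0.20.** If half of the discordant subjects keep being scanned, q is in effect 0.10 and the result is 34.5%. If instead half die inside the 95-day window, simulation gives 35.7%. At q = 0 there is no bias.

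**5. The exact test.** Two successes are needed for every n from 2 to 13, so counting censored subjects as failures or excluding them gives the same decision. Simulated rejection rates for q = 0.10, 0.20, 0.30:

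| Handling of censored subjects | True 2.6% | True 32% |
|---|---|---|
| Failure or excluded | 0.022, 0.022, 0.016 | 0.87, 0.86, 0.84 |
| Counted as progression-free | 0.13, 0.27, 0.40 | 0.93, 0.96, 0.98 |
| Kaplan-Meier rate turned into a count | 0.06, 0.12, 0.18 | 0.90, 0.92, 0.94 |

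**The case against.** **Imaging does not stop for everyone.** A reader might infer that every Investigator progression ends the scans. The documents do not support that: Protocol 7.2 and 8.10.1.3 continue them for subjects treated beyond progression. Those are subjects without clinical deterioration, for whom an IRC disagreement is plausible. This stands and narrows the point. Continuation is discretionary, however, and ends under 8.10.1.2.

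**Early deaths still count.** A death less than 95 days after the last adequate assessment, with no new systemic therapy, remains an event. This also stands; step 4 shows that it reduces the bias without removing it.

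**The test is not shown to be inflated.** A reader might infer that the 5% error rate is at risk. Neither document tells the analyst to count censored subjects as progression-free or to turn the Kaplan-Meier rate into a count, and only those routes exceed 0.05. The 84% power matches 9 evaluable subjects, which suggests exclusion. The charge of inflation therefore fails. What remains is that the rule is unwritten.

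**The modelled size is near a worst case.** Every discordant subject progresses by IRC at the next scan, and Investigator over-calls in subjects who would stay stable are not modelled. The shift of about 2.5 to 8 points at 32% is also smaller than the sampling error at n = 10, √(0.32 × 0.68/10) = 15 points. Both remarks are fair. Sampling error does not excuse a systematic upward shift, though.

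**PFS per Investigator already shows it.** Only in part. It applies the same long-gap censoring, leaves out progression seen only by the IRC, and counts Investigator progression even where IRC imaging continued. The per-protocol analysis repeats the primary censoring.

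**Conclusion.** The concern holds for a defined group: subjects who stop ivosidenib for Investigator progression without IRC progression and are not treated beyond progression. For them the stated rules end imaging, censor at the last adequate assessment, and can discard a known death before 6 months. That censoring is probably informative, and its direction is upward if Investigator calls tend to precede IRC calls.

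The size cannot be fixed from the documents. The ranges in step 3 rest on assumed discordance of 10% to 30% and on the near-worst-case model described there. The effect is smaller with continued scanning or early deaths, and nil without discordance. It concerns the Kaplan-Meier estimate. The exact binomial decision is unaffected, or slightly conservative, when these subjects are failures or excluded. The plan needs a targeted addition; its primary estimator and test can stay.

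**What to change.** **SAP 5.3.1.1.** Pre-specify a sensitivity Kaplan-Meier analysis of the 6-month rate on the ITT set. The event is the earliest of IRC progression, Investigator progression that ended imaging, or death from any cause, with no long-gap censoring of deaths. Report it beside the primary estimate.

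**SAP 5.3.1.** State that, for the exact test, two groups count as not progression-free: subjects known to have died before 6 months, and subjects whose imaging ended for Investigator progression before 6 months without an adequate later IRC assessment that settles their status. This changes no decision relative to exclusion, but it closes the routes that would inflate the error rate.

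**Table (5.3.1) 1.** Name the assessor in each row.

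**Cost.** SAP wording and one extra analysis on data already collected, with no additional scans. Protocol 10.1.2.3.1 already leaves censoring detail and further PFS analyses to the SAP. The sensitivity estimate is slightly conservative, because a subject called by the Investigator at week 24 and by the IRC at week 30 becomes an event before 6 months. In the step 3 model it equals p(1 − qh): 31.2%, 30.4% and 29.6% at a true 32% (simulated 31.2%, 30.6% and 29.4%). Set beside the primary estimate, it shows how far the result depends on these subjects.

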Adverse Events ²³			X	X	X	X	X	X	X	X	X		
Concomitant Medications and Procedures			X	X	X	X	X	X	X	X	X		
Survival Status and New Anticancer Therapy Check ²⁴													X

Abbreviations: AE = adverse event; ALP = alkaline phosphatase, ALT = alanine aminotransferase, aPTT = activated partial thromboplastin time; AST = aspartate aminotransferase; BUN = blood urea nitrogen; LDH = lactate dehydrogenase; D = Day; DNA = deoxyribonucleic acid; ECG = electrocardiogram, ECHO = echocardiography; ECOG = Eastern Cooperative Oncology Group; EOT = end of treatment; INR = international normalized ratio; LVEF = left ventricular ejection fraction; PD = pharmacodynamic; PFS = progression-free survival; PK = pharmacokinetic; PS = performance status; PT = prothrombin time; RBC = red blood cell; RECIST = Response Evaluation Criteria in Solid Tumours; RTSM = Randomization and Trial Supply Management; SAE = serious adverse event; WBC = white blood cell.

Note: all cycles are 28 days (±2 days) in duration, there are no planned rest periods between cycles.

*Results from the limited physical exams will be captured in source documentation, but there is no eCRF for these exams.

1. Assessments to be conducted within 5 to 33 days of last dose of study treatment.
2. At least 28 days, and no more than 33 days after discontinuation of treatment, subjects will return to undergo review of concomitant medications, ECOG PS, and assessment for resolution of any treatment-related toxicity.
3. Subjects who discontinue study treatment for reasons other than disease progression or withdrawal of consent and are alive by EOT will enter PFS follow-up with the same schedule of assessments as before study treatment discontinuation, until documented disease progression, death, start of subsequent anticancer therapy, or withdrawal of consent.
4. Subjects are to remain at the study centre for 6 hours following the C1D1 and C2D1 doses for PK/PD and ECG assessments.
5. If, at the discretion of the site, ICFs for pre-screening and main study part are taken separately
6. Height is to be obtained only at the Screening assessment.
7. On C1D1, assessment should be conducted pre-dose.
8. Systolic and diastolic blood pressure, heart rate, respiratory rate, and temperature. Assessments should be conducted while the subject is seated or supine. On C1D1, assessments should be conducted pre-dose.

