- Major protocol deviation if it interferes with the study evaluations and/or if it jeopardises participant's safety, e.g., any medical event requiring administration of an unauthorized concomitant treatment
- Withdrawal of consent (only for IMP discontinuation): subjects will be asked if they are willing to continue the safety and disease/survival follow-up.

All AEs should be followed until resolution or for a period of 28 days from the last dose of study treatment, whichever is shorter. If the subject withdrew from treatment because of an AE, every effort must be made to perform protocol-specified safety follow-up procedures.

Information to be collected during the last visit of these participants is given in [Section 5.5.2](#). These follow-up modalities are used to ensure the efficacy and safety evaluation of all participants who received the IMP.

Criteria for premature study discontinuation:

- Withdrawal of consent: Subjects may leave the study at any time for any reason if they wish to do so, without consequence. If a subject withdraws consent from overall study

participation (and not just study treatment), no further evaluations should be performed, and no attempts should be made to collect additional data.

- Death.
- Lost to follow-up.
- Study terminated by Sponsor.

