5.5.2. Procedure

In the case of premature study discontinuation due to an adverse event (event requiring immediate notification or not), the Investigator must make every effort to collect the information relating to the outcome of the event. If necessary, the information will be collected afterwards (see [Section 8.8.1.1](#)). This information is recorded in that part of the electronic case report form which concerns adverse events. If the Investigator cannot collect the information from a visit, he must collect it from the doctor ensuring the follow-up of the participant.

If the study is stopped / IMP is discontinued as a result of an event requiring immediate notification, the procedure described in [Section 8.8.1.5](#) is to be implemented.

The dispositions to be taken after the IMP discontinuation are described in [Section 6.5](#).

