8. ASSESSMENT OF SAFETY

All AEs and other situations relevant to the safety of the participants must be followed up and fully and precisely documented to ensure that the Sponsor has the necessary information to continuously assess the benefit-risk balance of the clinical trial.

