8.8. Reporting procedures

8.8.1. Time frame for AE reporting

- Any event meeting the above mentioned definitions (see [Sections 8.3](#) and [8.6](#)) must be reported to the Sponsor on an adverse event form if it occurred from the date the participant signs the information and consent form and: After informed consent has been obtained but prior to administration of the first IMP, only SAEs caused by a protocol-mandated intervention should be reported (eg, SAEs related to invasive study procedures such as biopsies).
- At any time after the first administration of IMP up to the participant’s last IMPs administration for all events regardless of attribution
- After the participant’s last IMP administration:
 - At least 28 days but no more than 33 days after the participant’s last IMPs administration for all AEs, regardless of the supposed role of the research.
 - Irrespective of the time of onset in case of serious AE related to the research.

[figure not shown]
¹ Instrumental Activities of Daily Living (ADL) refer to preparing meals, shopping for groceries or clothes, using the telephone, managing money, etc.

² Self-care ADL refer to bathing, dressing and undressing, feeding self, using the toilet, taking medications, and not bedridden”.

Of note, events occurring between the signature of the ICF and the first administration of the IMP for which the Investigator does not consider an association with the research must be reported **as medical history or as signs or symptoms related to the studied disease** in the dedicated form of the e-CRF.

Fatal events, related or not to the research, occurring after ICF signature and before first IMP administration, must be reported on AE form.

Figure (8.8.1) 1 - Rules for Adverse Event reporting

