8.8.1.2. Follow-up of adverse events

The Investigator must ensure that follow-up of the participant is appropriate to the nature of the event, and that it continues until resolution if deemed necessary.

Any change in terms of diagnosis, severity (improvement) intensity, seriousness, measures taken, causality or outcome regarding an AE already reported must be written up in a new complete evaluation of the event documented on the “Adverse event” page previously created for the event.

In case of worsening of severity, a new complete evaluation of the event must be documented on a new “Adverse event” form.

If the AE has not resolved at the participant's final visit, the participant must be followed up suitably and any information on the outcome of the event will be noted on the “Adverse Event” form previously created for the event.

If the follow-up of the participant is not done by the Investigator him/herself (hospitalisation, followed by a specialist or the participant's general practitioner, ...), the Investigator will do everything to establish/maintain contact with the person/department in charge of follow-up of the participant.

8.8.1.3. Special situations (pregnancy, overdoses, intake of IMP by a person around the participant)

Pregnancy

If a female participant in the study becomes pregnant, the Investigator must:

- stop immediately the study treatment,
- report it on the specific eCRF pregnancy form and notify the Sponsor immediately (i.e. without delay and within 24 hours of awareness at the latest),
- Pregnancy should not be reported as AE except in the following circumstances:
 - o If it is associated with an AE. This consequence itself should be reported as an AE.
 - o While pregnancy itself is not considered to be an AE, any pregnancy complication or elective termination of a pregnancy for medical reasons will be reported as an AE. Abnormal pregnancy outcomes (e.g. spontaneous abortion, death, stillbirth, congenital anomalies, ectopic pregnancy) are considered SAEs and will be reported as such.
- contribute to the follow-up of this pregnancy and provide the Sponsor with information concerning this follow-up (notably using the 2nd page of the specific paper pregnancy form).

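### Protocol Section 5.5.1 ends follow-up of every adverse event by day 28 after the last dose, in conflict with Section 8.8.1.2 for events still open at the final visit

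*Protocol*

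**What the plan says.** Two protocol sections set a rule for how long adverse events are followed.

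- **Section 5.5.1 (Withdrawal criteria)**, in the part on stopping study drug: "All AEs should be followed until resolution or for a period of 28 days from the last dose of study treatment, whichever is shorter".
- **Section 8.8.1.2 (Follow-up of adverse events)**, for an event not resolved when the participant makes the final visit: "the participant must be followed up suitably and any information on the outcome of the event will be noted". No day limit is attached.

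Other texts bear on the point without settling it.

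- Section 5.5.1 also says: "If there is a medical reason for withdrawal, the subject will remain under the supervision of the Investigator until satisfactory health has returned". For a subject who stopped treatment because of an adverse event, it adds that "every effort must be made to perform protocol-specified safety follow-up procedures".
- Section 5.5.2, for study discontinuation due to an adverse event: "the Investigator must make every effort to collect the information relating to the outcome of the event".
- The opening of Section 8: "All AEs and other situations relevant to the safety of the participants must be followed up and fully and precisely documented".
- Footnote 2 to the investigation schedule in Section 4.1.2, on the safety visit: "subjects will return to undergo review of concomitant medications, ECOG PS, and assessment for resolution of any treatment-related toxicity".
- Section 8.8.1 sets the reporting window for adverse events regardless of cause: "At least 28 days but no more than 33 days after" the last administration. Related serious events stay reportable whatever their time of onset.

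**The concern.** The wording of 5.5.1 makes 28 days a ceiling, because the shorter of the two periods applies. It cannot be read as a minimum. For an event that is still open on day 28, 5.5.1 says follow-up is over and 8.8.1.2 says it must go on. Neither section refers to the other, and no order of precedence is given.

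A site that works from 5.5.1 could stop following an unresolved toxicity at day 28 and leave its outcome blank. SAP Appendix B treats an adverse event with a completely missing end date as ongoing, so an event that resolved after the limit could stand in the listings as never resolved. Safety and tolerability is a secondary objective, and with about 10 subjects each outcome carries some weight.

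**Working it through.** The plan gives no figure on this point to reproduce. The check sets the rules side by side and counts days, with the last dose as day 0.

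| Text | Applies to | End of follow-up | Force |
|---|---|---|---|
| 5.5.1, day limit | all adverse events | min(resolution, day 28) | should |
| 8.8.1.2, unresolved events | events open at the final visit | none stated; outcome to be recorded | must |
| 8.8.1.2, general sentence | all adverse events | resolution, where judged necessary | must |
| 5.5.1, supervision | withdrawal for a medical reason | return to satisfactory health | will |

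**Step 1: timing against the safety visit.** Sections 4.1.1 and 4.1.2 place this visit 28 to 33 days after the last dose. Visit day minus the 5.5.1 limit is 28 − 28 = 0 days at the earliest and 33 − 28 = 5 days at the latest. For an event found open at that visit, 5.5.1 leaves 0 further days, while 8.8.1.2 requires follow-up if this is the final visit. If the final visit is a later one, for example in PFS follow-up, the 5.5.1 limit passed longer ago.

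**Step 2: can the two rules be reconciled?** Section 8.8.1.2 leaves general follow-up to resolution partly to judgement. That qualifier is in its opening sentence. The later sentence on events unresolved at the final visit carries no such qualifier, so it does not remove the conflict.

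**Step 3: would the situation arise?** Section 8.10.1.1 allows dosing to be held for up to 28 days for an adverse event and, with possible exemptions, calls for discontinuation if dosing cannot resume in that time. In that case the time left under 5.5.1 when the decision is made is about 28 − 28 = 0 days. The limit then falls just as a subject is discontinued for non-recovery.

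**Step 4: late related serious events.** Section 8.8.1 makes these reportable at any time. One with onset after day 28 has no follow-up period under 5.5.1.

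**Step 5: what the analysis uses.** SAP Section 5.4.1 defines a treatment-emergent event by its occurrence between first dose and last dose + 28 days. Its planned tables use term, grade, seriousness, relation to drug, action taken and, for QT events, time to onset. None uses resolution. The primary test is of the 6-month PFS rate and uses no adverse event data.

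**The case against.** The best reply is that a careful site would never go wrong. Nothing forbids follow-up beyond day 28. Section 8.8.1.2 is the section dedicated to the subject and is mandatory where 5.5.1 is advisory. It also applies whatever the reason for stopping. The safety visit checks resolution of treatment-related toxicity at about the time the limit falls. All of this stands and keeps the point small. It does not make the two rules agree, since a site that follows 5.5.1 as written reaches a different stopping point.

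A reader might infer three stronger things that the documents do not support.

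- *Section 5.5.1 plainly contradicts itself.* The supervision sentence covers only withdrawal for a medical reason, and it can mean clinical care that continues after data collection has ended. It is secondary support only.
- *The day limit is an isolated slip against everything else in the protocol.* Section 4.1.2 describes the day 28 to 33 visit as serving final safety assessments, and Section 6.1.1 speaks of a 28-day safety follow-up window. The figure recurs. Section 5.5.2 and the opening of Section 8 ask for outcomes and documentation but state no duration, so they do not set a competing time limit.
- *Open events would be abandoned.* The protocol does not require that. The risk is that a site may stop, not that it must.

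**Conclusion.** The conflict between Sections 5.5.1 and 8.8.1.2 is real and direct for any adverse event open at the final visit, and the protocol does not resolve it. It is minor. What is at stake is safety follow-up and the completeness of outcome data in about 10 subjects, with no effect on the primary test or on treatment-emergent event counts.

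The number of events affected cannot be estimated, because the documents do not say how many are expected to be open at day 28. A single subject may have several. The conclusion rests on reading the 5.5.1 sentence as applying to all adverse events, as it says. It does not extend to subjects who withdraw consent from the whole study, since 5.5.1 bars further data collection for them.

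**What to change.** Replace the 5.5.1 sentence with:

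> New AEs are collected as specified in Section 8.8.1 (up to 28 to 33 days after the last dose; related SAEs irrespective of time of onset). AEs ongoing at the safety follow-up visit or at the participant's final visit are followed per Section 8.8.1.2 until resolution, stabilisation, death, loss to follow-up, end of study or withdrawal of consent from overall study participation, and the outcome is recorded on the AE form.

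This separates the window for collecting new events from the follow-up of open ones. It covers both the safety visit and a later final visit, gives follow-up a definite end, and respects full withdrawal of consent. No SAP change is needed. The cost is one sentence of protocol wording and a few additional outcome updates.
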